6.2 Study Device Dispensing

The DBS system will be acquired from Medtronic Inc. (as above). The DBS leads will be surgically implanted by the neurosurgical team. The neurostimulator will be implanted in an outpatient surgical procedure, 7-10 days after lead implantation. We will follow the same standard of care procedures followed for implantation of DBS for Parkinson's disease (e.g., device identification number will be verified and recorded in the study records).

6.3 Intervention Delays and Modifications

If a participant experiences adverse effects related to stimulation, we will modify the stimulation parameters until the adverse effects have resolved.

If the adverse effects are refractory to DBS optimization, this will call for early explantation of the DBS system. There will not be modifications to the study device itself (both electrodes and stimulator are implanted).

6.4 Study Device Compliance

Participants can turn off the DBS system (Percept stimulator). This ability is given to them in case they experience delayed severe adverse effects while away from the clinical setting. The study team can monitor the device logs to know exactly when and for how long the device was turned off. DBS therapy is supposed to be continuous. If the device logs show that participants are turning off the device independent of adverse effects > 50% of the time, we will discuss with the participants the importance of keeping the DBS on all the time, and if this issue persists, we will withdraw the subject from the study and explant their DBS system.

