5.1 Subject Population

The goal is to implant DBS in 3 participants (male and female), 21-75 years old, with severe AUD and advanced liver disease (stage 3 liver fibrosis, or compensated cirrhosis/stage 4 fibrosis), living in Western Pennsylvania. Due to potential screen fails, 3-10 subjects will be enrolled (consented) and screened. We will stop enrolling subjects when 3 participants are implanted with DBS. This study will not include vulnerable populations; only adults (>21) with the capacity and competence to fulfill informed consent will be allowed to participate.

All Participants will be referred to an outpatient addiction clinic to receive standard of care AUD treatment. We will keep track of the treatments received by every participant throughout the study duration.

Inclusion/exclusion criteria were chosen to maximize both patient safety and the benefit-to-risk ratio, given the invasive nature of this study.

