7.7 Early Discontinuation Safety Assessments

Similarly to end-of-study, participants who are withdrawn from the study early will undergo explantation surgery of the DBS system. Again, these patients will be monitored overnight after surgery, and will receive a post-operative CT scan to ensure there are no complications. A follow-up visit with the neurology/neurosurgery team will be scheduled 2 weeks later to ensure safety. They will have 3 monthly follow-up visits after DBS explantation. They will then be referred to outpatient psychiatry clinic for standard of care follow-ups.

8 Potential Risks and Benefits

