11.2 Other Criteria Requiring Discontinuation

If participants turn their DBS system off more than 50% of the time, which is unprompted by adverse effects, and if they continue to turn it off after discussion with the team, they will be withdrawn from the study and their DBS explanted.

Beginning chemotherapy or other investigational medications after enrollment will result in the subject's discontinuation from the study.

Beginning anticoagulation after enrollment and before DBS implantation will result in the subject's discontinuation from the study.

If a patient no longer wishes to continue their participation in the study, they may elect to withdrawal from the study. Normal recruitment procedures will resume to replace any participant withdrawals (see recruitment description in section 5.4).

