12.1 General Approach

The general analysis plan begins with data description, including basic summary statistics such as means, standard deviations, correlations, cross-tabulations, and checking for outliers and missingness patterns. Data will be evaluated for normality through goodness-of-fit tests and q-q plots. If systematic deviations from normality are detected, the corresponding variables will be appropriately transformed using logarithm or other Box-Cox transformations.

We will examine spaghetti plots for visualization of the individual trajectories over time for the longitudinal hypothesis. The analyses for the longitudinal data will consist of computation of summaries across time and at each time point. For any fitted models, we will evaluate uncertainty in the model parameter estimates and assess goodness of fit for each model using standard techniques such as residual analysis and regression diagnostics.

For testing hypotheses we will use standard methods such as the t-test; we will use the Wilcoxon and chi-square tests when appropriate. With small sample size, we will use exact methods to compute the significance level. For testing proportions, we will use the standard arcsin transformation of proportions to stabilize variance and improve the normal approximation.

For each analysis discussed, we will also consider models that control for socio-demographic descriptors for the individuals in the study when available.

Missing data:

We will enroll a replacement participant if withdrawal occurs. To account for missing data, we will use inverse weighted probability analyses and imputation-based methods, and conduct sensitivity analysis to assess the stability of conclusions across analyses.

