12.4 Analysis of Secondary Endpoints

The secondary outcomes are:

- 1) *Alcohol use* measured as PDA, DDD, PEth, GGT at baseline and monthly after DBS implantation.
- 2) *Overall functioning* and disability measured with the WHODAS 2.0 scale at baseline and monthly after DBS implantation.
- 3) *Target engagement* measured with FDG-PET scans at 3 time points: pre-DBS baseline, post-DBS-OFF, and post-DBS-ON at 6 months.

The secondary outcome *PDA* as a measure of *alcohol use* is a proportion, collected at baseline and during follow-up and assessment visits (1 baseline and 12 monthly post-DBS measurements).

The other measures of alcohol use (*DDD, PEth, GGT*) and the overall functioning score *WHODAS 2.0* are continuous variables collected at baseline and during follow-up and assessment visits (1 baseline and 12 monthly post-DBS measurements).

Alcohol use and overall functioning

H3: LP DBS reduces alcohol use and improves overall functioning in subjects with severe AUD compared to baseline. Specifically, LP DBS increases PDA, and decreases DDD, PEth, GGT and WHODAS 2.0 score compared to baseline.

Primary analysis of H3: We will compare the baseline and 6-month time point using a paired t-test for each of the measures (PDA, DDD, PEth, GGT and WHODAS 2.0).

For PDA, the unit of analysis is the proportion of days X_{ij} in a month that participant i is abstinent during month j . To do the paired t-test, we use the two paired proportions X_{i0} (0 refers to the baseline measure) and X_{i6} (6 refers to the 6-month measure). We can use a t-test on the difference $D_i = (X_{i6} - X_{i0})$. This should be a reasonable approximation because the averages X over roughly $n = 30$

days should be approximately Gaussian. The Gaussian approximation can be improved by using the variance stabilizing transformation

$$Y_{ij} = 2 \arcsin \sqrt{X_{ij}}$$

Thus, we will do a t-test using the differences $2[\arcsin \sqrt{X_{i6}} - \arcsin \sqrt{X_{i0}}]$. With $n = 3$ participants, we have little power unless the effect is large (e.g., if PDA moves from 0.05 to 0.50).

Secondary analysis of H3: To assess the course of PDA, DDD, PhEt, GGT, and WHODAS 2.0 over the duration of the study while taking into account the repeated measures (13 measures for each participant – one at baseline and 12 post-DBS), we will use a **mixed-effects model**:

$$Z_{ij} = \mu + \alpha_i + \tau_j + \epsilon_{ij}$$

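### Withdrawal for persistent device non-use, chemotherapy or another investigational medication ends calendar-based outcome collection, and the plan does not say how withdrawn and replacement participants enter the analyses

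*Protocol*

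**What the plan says.** Protocol section 6.4 concerns participants who are "turning off the device independent of adverse effects > 50% of the time". The team first discusses the matter with them. If it persists, "we will withdraw the subject from the study and explant their DBS system". Section 11.2 repeats the rule ("they will be withdrawn from the study and their DBS explanted") and also discontinues from the study anyone who starts chemotherapy or another investigational medication after enrolment.

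Section 7.7, headed as safety assessments, covers everyone withdrawn early: explantation, a neurology/neurosurgery visit 2 weeks later, and then "They will have 3 monthly follow-up visits after DBS explantation", followed by referral to standard care. It schedules no month-6 or month-12 outcomes.

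On replacement, section 11.2 says "Normal recruitment procedures will resume to replace any participant withdrawals". Section 12.1 of the Protocol and SAP opens its missing-data paragraph with "We will enroll a replacement participant if withdrawal occurs", then names inverse probability weighting, imputation and sensitivity analysis. Section 5.1 says "We will stop enrolling subjects when 3 participants are implanted with DBS".

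For H3, section 12.4 says "We will compare the baseline and 6-month time point using a paired t-test", with a mixed model over months 0 to 12 as the secondary analysis. H2.b in section 12.3 requires more than 80% of follow-up visits and assessments to be completed. No analysis set is defined; intention-to-treat appears only in the abbreviation list.

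**The concern.** For these withdrawal routes the protocol treats leaving the device and leaving the study as one event. The alcohol and functioning outcomes are fixed to the study calendar, whereas follow-up after withdrawal is fixed to the explantation date. A participant who leaves early and would gladly go on giving drinking histories and blood samples is not scheduled to give them at the analysis time points.

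Why someone persistently switches off, or turns to another experimental treatment, may be connected with how they are doing, so the missing values may be informative. Section 6.1 says it is unclear whether turning stimulation off or explanting leads to relapse, and these participants could help answer that. With three participants, each is a third of the evidence. A reader of the final report also could not tell whether H3 and H2.b describe everyone implanted or only those who completed.

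**Working it through.** **Inputs.** From Appendix A, whose table is broken in the available text: stimulation starts about Day 50-51; the month-6 assessment begins on Day 230 ± 7 and the month-12 assessment on Day 412 ± 7. From section 7.7: three monthly visits, taken as ending 90 days after explantation (30-day months assumed). From section 12.4: 13 measures for each of 3 participants, and an example effect of PDA 0.05 to 0.50.

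**The plan's own figure.** 3 × (1 baseline + 12 monthly) = 39 measures, as stated. This count leaves no place for a partly observed fourth implanted participant.

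**When the time points are lost.** The last visit falls at about E + 90 for explantation on day E.
- Month 6 is out of reach if E + 90 < 230 − 7, that is E < 133, roughly the first 80 days of stimulation.
- Month 12 is out of reach if E + 90 < 412 − 7, that is E < 315.
- Between about Day 133 and month 6, a visit near month 6 remains, off the device. Withdrawal after the month-6 assessment keeps month 6.

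**If the lost participant is not replaced.** The 95% confidence half-width for the mean change, in SDs of the change, is t/√n.
- n = 3: 4.303/√3 = 2.48
- n = 2: 12.706/√2 = 8.98
- Ratio: 8.98/2.48 = 3.6

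The section 12.4 example gives an arcsine difference of 2(arcsin√0.50 − arcsin√0.05) = 1.12. Power from the noncentral t, with two-sided alpha 0.05 and the SD of differences both assumed:

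| SD of differences | n = 3 | n = 2 |
|---|---|---|
| 0.3 | 88% | 32% |
| 0.5 | 54% | 20% |
| 1.0 | 21% | 10% |

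**If the lost participant is replaced.** Assume month-6 PDA of 0.50 in the two retained participants and in the replacement.

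| Withdrawn participant's PDA | Replacement substituted | First 3 implanted | All 4 implanted |
|---|---|---|---|
| 0.05 | 0.50 | (0.50 + 0.50 + 0.05)/3 = 0.35 | 1.55/4 = 0.39 |
| 0.20 | 0.50 | 1.20/3 = 0.40 | 1.70/4 = 0.425 |
| 0.50 | 0.50 | 0.50 | 0.50 |

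The last row shows that there is no distortion if the withdrawn participant did as well as the others. This scenario and the previous one are alternatives and cannot both apply to the same loss.

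**Feasibility (H2.b).** Assume completion is pooled over 12 monthly visits each, the other two participants complete all 24, and post-explantation visits are not counted. Withdrawal after month 4 gives (24 + 4)/36 = 78%, a failure; after month 5, 29/36 = 81%, a pass. If the replacement's visits count instead, the figure can be 100%.

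**The case against.** A reader might infer that anyone who stops stimulation is withdrawn, that exactly the treatment failures are lost, and that replacements who stay on stimulation take their place. The documents do not support that reading.

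- The non-use rule needs more than 50% off time, no adverse-effect reason, and persistence after discussion.
- Continued craving or relapse leads to re-titration (section 6.1). Sustained increased drinking leads to the device being turned off and the DSMB consulted (section 9.1). Explantation for lack of benefit is placed at the end of the study (section 6.1). Relapsers and non-responders therefore remain.
- Adverse effects that do not respond to parameter changes go to the DSMB, which considers removal and withdrawal (section 13.4).
- Replacements face the same rules, and section 5.1 read literally would bar replacing an implanted participant.
- No text says a withdrawn participant's data are discarded, and missing-data methods are named.
- The content of the three post-explantation visits is not stated. Section 7.5 says follow-up assessments match section 7.4, which includes the Timeline Followback (TLFB) drinking history and blood markers; whether that reaches the section 7.7 visits is unclear.

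It is also fair that H3 is secondary in a pilot that admits little power, and that meeting the non-use rule and being explanted before Day 133 would need a rapid sequence of events.

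All of this narrows the point without removing it. Weighting and imputation have no stated model and cannot be credibly estimated from three people. The section 5.1 conflict does not help either: if enrolment stops, n = 2 remains for month 6 after an early loss; if it resumes, the role of the replacement is undefined.

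**Conclusion.** The point holds in this limited form. For participants withdrawn under sections 6.4 and 11.2, calendar-based outcome collection is not continued. Month 6 falls outside follow-up when explantation comes before about Day 133, and month 12 when it comes before about Day 315. The plan does not define how withdrawn and replacement participants count in H3 or in H2.b, which is part of a primary outcome. Adverse events are also observed for less time in these participants.

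The loss may be informative, but its direction is not known from the documents. The cut-off days rest on a broken Appendix A table, 30-day months and the 7-day window. The PDA, power and completion figures rest on the assumed values shown and illustrate size only. It is a change worth making because it is inexpensive and addresses a loss that no analysis of three people can repair afterwards.

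**What to change.** Leave the stopping and explantation rules unchanged.

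1. In Protocol sections 6.4, 7.7 and 11.2, separate discontinuation of the device from withdrawal of consent to follow-up.
2. Unless consent is withdrawn, keep every implanted participant on the original calendar for TLFB, PEth, GGT, WHODAS 2.0 and adverse-event review through months 6 and 12. Section 7.4 already allows TLFB to be taken during the weekly phone calls.
3. In sections 12.3 and 12.4 of the Protocol and SAP, analyse all implanted participants whatever their device status, count them in the completion rate, and report any replacement as an additional participant.
4. Reconcile the enrolment stop in section 5.1 with the replacement rule in sections 11.2 and 12.1.

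Cost: a protocol amendment with consent wording, and a few visits and blood draws of existing types per discontinued participant. PET scans and device-dependent tasks need not be added. The efficacy estimate may come out less favourable.

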6.5 Study Device Storage and Accountability

Between receipt of the DBS system and surgical implantation, the DBS system will be stored in the office of the principal investigator or the neurosurgeon MPI, which is separate from where the clinical supply is stored. Upon completion of the study, if the system is explanted, it will be disposed of.

6.6 Prohibited Medications

Patients receiving treatment with another investigational drug or intervention within three months will be excluded from participation. Patients with implanted devices/hardware (e.g., pacemakers, metal) which interfere with the ability to perform brain MRI will also be excluded (outlined in exclusion criteria).

List of prohibited medications:

- Anticoagulants (heparin, warfarin, or other oral anticoagulants like apixaban, rivaroxaban, dabigatran).
- Chemotherapy medications.
- Investigational medications for AUD that were started within the last 3 months before the trial.

6.7 List of allowable medications

Any medications not included in the prohibited medication list in section 6.6.

[figure not shown]
6.8 Breaking the Blind

Not applicable – study is not blinded.

7 Research Activities

Schedule of research activities is provided in Appendix A.

Overview of study design:

7.1 Screening Procedures

Pre-screening: Potential participants will undergo initial IRB-compliant pre-screening. For patients approached by a study investigator in an inpatient or outpatient clinic setting, pre-screening will occur in person at the time of recruitment. For patients who established contact over phone or email, pre-screening will be performed over the phone. Pre-screening will collect contact information, age, severe AUD diagnosis by DSM-V criteria, self-attestation of any medical, neurologic, or psychiatric diagnoses that might disqualify the potential participant from the study. We will also administer the Insight (SOCRATES) questionnaire and ask about prior AUD treatments. After initial pre-screening, potential participants will be scheduled for in-person consent and eligibility-screening.

The screening and baseline visits will occur over approximately a 4-20 day period. Depending on the resources and personnel availability, some procedures or assessment may occur on a different day than described. Refer to the Schedule of Activities in Appendix 1 for a comprehensive listing of all study procedures and assessments.

Consent and Eligibility Screening: The study coordinator will begin by reviewing the consent form with the potential participant. A physician investigator will answer any questions and ensure the participant understands the study rationale, procedures, and potential risks and benefits (outlined in the IRB-approved consent form), before the consent is signed. After each participant signs the consent form, the physician will sign the Investigator's Certification statement on the consent form. Signed consents will be stored under two sets of locks, and a copy will be provided to the participant. Participants will then undergo a diagnostic and eligibility evaluation that includes:

1. Blood tests – complete blood count (CBC: red blood cell count, white blood cell count, platelet count), complete metabolic panel (CMP: Glucose, Calcium, Sodium, Potassium, Bicarbonate, Chloride, Blood urea nitrogen, Creatinine, Albumin, Total protein, Alkaline phosphatase, Alanine aminotransferase, Aspartate aminotransferase, Bilirubin), coagulation tests (INR, PT, PTT, platelet function test, fibrinogen activity, fibrinogen antigen, thrombin time, reptilase time, thromboelastography), pregnancy test, and makers of chronic alcohol use (blood phosphatidylethanol (PEth) and blood gamma-glutamyl transferase (GGT)). We may also check liver fibrosis blood test panel to diagnose liver fibrosis in some cases (e.g., body habitus does not allow accurate liver elastography or if there is difficulty scheduling liver elastography). Some of the blood tests may occur during the baseline evaluation days. We will repeat the following blood tests on the morning of the surgery (INR, PTT, CBC, thromboelastography).
2. Imaging – structural brain MRI (3-Tesla, with contrast) and liver ultrasound; the MRI may be deferred if already available in the EHR from the last 2 years. The liver US may be deferred if subject is already diagnosed with liver fibrosis stage 3 or 4 or if liver fibrosis blood panel is used instead. Subjects to receive a liver ultrasound in the morning are asked to omit all food and fluids (except water and medications) from midnight the night before the liver ultrasound. Subjects scanned later in the day are asked to omit food and fluids (except water and medications) for at least 4 hours prior to the liver ultrasound.
3. Clinical evaluation – medical (including EKG), neurologic, and psychiatric (including a Structured Clinical Interview for DSM-5).

If all inclusion and exclusion criteria are met after evaluation, participants will be enrolled in the study and will be scheduled for pre-DBS baseline assessment. Participants will be asked to detox and abstain from alcohol use for at least 7 days prior to the DBS surgery.

In addition, during the screening, eligibility assessments, and pre-DBS evaluations, participants will be screened to ensure they are not intoxicated, and they will undergo formal mental status examination (part of psychiatric evaluation) and a detailed neuropsychological evaluation by a trained clinical neuropsychologist to ensure they have the necessary mental capacity and are competent to sign the informed consent. If the mental status or the neuropsychological evaluations show that the participant in question is not competent, they will not be allowed to continue in the study.

7.2 Randomization/Study Entry Procedures

Randomization will not be necessary as there is only one study arm.

7.3 Study Device Intervention

Refer to section 6 of the protocol for information on use of the study device. Also refer to section 6.3 for instruction on intervention delay and modification.

7.4 Safety and Efficacy Assessments/Procedures During Intervention

- **Clinical evaluations:** medical, neurologic, psychiatric, and neurosurgical evaluations will be obtained by Board-Certified clinicians in their respective specialties. The initial psychiatric evaluation includes a SCID-5 (Structured Clinical Interview for the DSM-V for research) and questions about what alcoholic beverages the subjects usually consume, which will be performed by the study psychiatrist or trained study staff. Follow-up psychiatric evaluations include CIWA scale and mental status examination. These evaluations are important to ensure participants meet eligibility criteria and to screen for any DBS adverse effects after the DBS is turned on.
- **Electrocardiogram:** this is standard-of-care clinical ECG; we will obtain it as part of the medical evaluation to ensure participants are fit for surgery.
- **Blood tests:** a qualified and well-trained nursing or other CTRC staff will obtain standard-of-care peripheral blood samples to test for liver function, blood coagulation, kidney function, pregnancy, and for markers for chronic alcohol use. Some of these tests are necessary for the safety of participants (e.g., liver function tests will help ensure participants are not in full liver failure, complete blood count to ensure platelets are not deficient, etc). Other tests are necessary to measure the outcomes of the study (e.g., blood markers of chronic alcohol use).
- **Urine tests:** urine drug screens and urine pregnancy tests will be obtained to screen for non-alcohol substance use and for pregnancy, respectively.
- **Breathalyzer tests:** obtained to estimate alcohol blood levels during evaluations, to ensure participants are not intoxicated.
- **Brain MRI:** tractography MRIs will enable surgical planning to target the DBS electrode to the desired brain region. Structural MRI after DBS implantation will allow accurate localization of DBS electrodes if this could not be clearly estimated from the post-op CT scan due to excessive artifact.
- **Head CT scans:** will be obtained to help with target planning (CT will be fused to the MRI image), and to ensure lack of bleeding and correct placement of the DBS electrode after surgery. 3 CT scans will be obtained (pre-op, post-op, and at the end of study – after DBS electrodes are

explanted). Low dose CT scans will also be obtained during PET imaging for attenuation correction.

- **PET scans** (Positron emission tomography): [¹⁸F] fluorodeoxyglucose- (FDG) PET scans will be obtained pre- and post-DBS to assess target engagement and DBS-induced functional changes in brain circuits associated with AUD. Subjects to receive a PET FDG scan in the morning are asked to omit all food and fluids (except water, medications) from midnight the night before the FDG scan. Subjects scanned later in the day are asked to omit food and fluids (except water, medications) for at least 4 hours prior to FDG injection. Upon arrival to the imaging center, compliance to the dietary requirements will be confirmed and blood glucose level should be checked. Blood glucose level should be < 175 mg/dL (7.8 mmol/L). If blood glucose level >175 mg/dL, rescheduling the subject will be considered. If this is not an option, the scan will continue and a note will be made on the PET assessment form in the appropriate comment line following the blood glucose record.
- **Contraception:** Female participants with reproductive potential will be asked to use an effective method of contraception (birth control) from at least 4 weeks prior to DBS surgery until the end of the study in order to avoid exposing fetuses to radiation (see below), surgery and anesthesia, and unknown effects of DBS on fetuses. Choice of contraception will be decided by the participant in consultation with her PCP or OB/Gyn doctor.
- **QUESTIONNAIRES:** a variety of questionnaires are administered for various purposes as described below:
 - **AUD assessment:** this will be based on 4 questionnaires
 - 1) **Alcohol Timeline Followback** (TLFB): uses a calendar with some memory aids (e.g., drinking diary) to obtain estimates of daily drinking prior to interview date. We will use it to assess drinking over 180 days (for baseline pre-DBS assessment) or 30 days from the interview date (for follow-up visits, 6-, and 12-months post-DBS assessments). All study personnel administering TLFB will have proper training. If subjects have difficulty remembering their alcohol consumption over a 30-day period at a time, we will assess drinking on a weekly basis during the weekly phone call for MADRS (see below).
 - 2) **Alcohol Craving Questionnaire-Short Form** (ACQ-SF-R): 12-item questionnaire that measures 4 dimensions of alcohol urges and craving (Emotionality, Purposefulness, Compulsivity, and Expectancy); usually completed within 5 min.
 - 3) **Alcohol dependence scale** (ADS-25): 25-item questionnaire that assesses the severity of alcohol dependence based on questions that cover withdrawal symptoms, impaired control, insight into compulsive drinking, tolerance, and drinking related behaviors; usually completed within 5-10 min.
 - 4) **Obsessive Compulsive Drinking Scale** (OCDS): 14-item questionnaire that is sensitive and specific for the obsessive and compulsive aspects of drinking (thoughts, urges, ability to resist the urges); usually completed within 5-10 min.
 - **Overall functioning and disability.** For this assessment, we will use the **World Health Organization Disability Assessment Schedule 2.0** (WHODAS 2.0) questionnaire. This is a 36-question self-administered questionnaire recommended by the DSM-5 to evaluate overall functioning and disability given its high reliability [141]. The questions survey 6 domains related to the participant's wellbeing including cognition, mobility, self-care, getting along, life activities, and participation in society [152].
 - **Mood and anxiety assessments:** these questionnaires aim to screen for any adverse effects of DBS on mood and anxiety.

1) Montgomery Asberg Depression Rating Scale (MADRS): this is a 10-item scale widely used in clinical trials to screen for and assess depression severity. This will be administered weekly over the phone, and monthly during in-person follow up visits. If the phone screening shows a score that is 6 points higher than the previous screening or if it shows severe depression (>35), a study physician will evaluate the participant over the phone and decide if the participant needs to come in for an in-person urgent assessment for further evaluation and risk stratification.

2) Mood and Anxiety Symptom Questionnaire (Mini-MASQ): This is a 26-item scale (~15 min) that assesses 5 subscales of depression and anxiety including anhedonia.

3) Hamilton Anxiety Rating Scale (HARS): this widely used 14-item scale screens for general anxiety.

4) Apathy Evaluation Scale (AES): this is an 18-item scale administered over 10-20 min to screen for apathy by evaluating motivated goal-directed behaviors.

5) Young Mania Rating Scale (YMRS): this is an 11-item scale to screen for manic or hypomanic symptoms. This is usually completed within 5 min.

- **Suicidality:** the Columbia-Suicide Severity Rating Scale (C-SSRS) will be used to assess suicidality to improve safety monitoring.
- **Pittsburgh Sleep Quality Index (PSQI):** This 10-questions self-rated questionnaire assesses overall sleep quality over the month prior to its administration. This is usually completed within 5 min.
- **Impulsivity and reward sensitivity questionnaires:**

1) Urgency, Premeditation, Perseverance, Sensation seeking, Positive urgency, Impulsive behavior Scale (UPPS-P): this is a 59-item questionnaire that evaluates the different dimensions of impulsivity including the tendency to act under extreme negative or positive emotions, tendency to act without thinking, inability to focus on one task, and tendency to seek novel experiences. This will be used to evaluate DBS effects on impulsivity.

2) Behavioral Inhibition System/Behavioral Activation System Scale (BIS/BAS): this scale is a 24-item self-report questionnaire that evaluates both the motivation to approach rewarding stimuli and the motivation to avoid aversive outcomes. This will be used to evaluate DBS effects on behavioral activation and inhibition.

- **Insight:** this will screen for participants' insight into their drinking problem.
 - Recognition subscale of the Stages of Change Readiness and Treatment Eagerness Scale (SOCRATES V.8)[153] (<5 min).

- **Electroencephalogram (EEG):** will be recorded during one of the behavioral tasks (Card Guessing Task, see below) (6 - 66 scalp sites, one below the right eye, and one at the nose tip). The EEG is needed as a physiological readout of the behavioral task.

- **Neuropsychological evaluation:** this is a standard neuropsychological evaluation done to ensure the participants have the cognitive capacity to understand the consent process, and to screen for any effects of LP DBS on the various cognitive domains (language, executive, visuospatial, learning and memory). This evaluation is administered as a combination of pencil and paper tasks and questions/answers format. This evaluation includes the following assessments:

1) Orientation (~2 min): this provides a measure of the participant's mental state and attention.

2) Wechsler Test of Adult Reading (WTAR) (~5 min): provides a measure of intelligence.

3) Trail Making Test parts A and B (~3-8 min): tests processing speed.

4) Repeatable Battery for the Assessment of Neuropsychological Status (RBANS) which includes list learning, story learning, copying a complex figure, line orientation task, picture naming task, coding task, digit span forward task, delayed recall of the learned list, delayed recall of the learned story, and delayed recall of the copied figure (~30 min): this assessment provides a measure of language and visuospatial functions.

5) Controlled Oral Word Association Test (~5 min): this provides a measure of verbal fluency. The timed task requires the participant to name as many words as possible that begin with a specified letter.

6) Digit Span from the Wechsler Adult Intelligence Scale- 4th Ed (backward and sequencing) (~5 min): this test provides a measure of working memory.

7) Vocabulary, Similarities, and Matrix Reasoning of the Wechsler Abbreviated Scale of Intelligence (~20-40 min): this provides a measure of language and executive functions.

- **Cognitive and behavioral tasks:** these tasks are used to measure cognitive and behavioral processes strongly associated with vulnerability to relapse to alcohol like cue reactivity, reward processing, and various aspects of impulsivity. These tasks are administered via a computer screen and the participants are required to press a button or keyboard stroke, or fill a paper questionnaire after presentation of cues on the screen. These tasks are described in detail in the Research Strategy Section and include:
 - 1) Alcohol Cue Reactivity task (CR).** This task measures reactivity and craving in response to alcohol cues. Participants will be seated in front of a computer screen and will complete a 12-trial computer-automated CR procedure. Each trial consists of a relaxation prompt, a picture cue presentation (alcohol vs. neutral; the alcohol cues are informed by subjects' drinking preferences collected during the psychiatric evaluation), and a final prompt to fill out post-trial self-report ratings of craving, mood, and arousal based on how he/she felt while focusing on that picture. The CR task lasts approximately 15 minutes.
As exposure to alcohol cues could cause craving, anxiety, and discomfort. Experienced Psychiatry Department study staff will be present at all times during cue exposure and will provide support and conduct relaxation techniques until craving returns to pre-exposure levels.
 - 2) Card Guessing Task (CGT).** This task measures reward processing. The CGT consists of up to 240 trials (3-trial types; ~23 min) coded in Neurobehavioral Systems Presentation. Trials occur in the setting of alcohol vs. neutral cues. Subjects are asked to press one of two buttons indicating whether a card will show a low (1-4) or high (6-9) number. EEG will be recorded during the CGT.
 - 3) Balloon Analog Risk Task (BART).** This task measures propensity for risk taking. A total of up to 350 trials will be performed. Trials will occur in the setting of either an alcohol-related or a neutral cue, followed by an image of a deflated red balloon. The participant will then press a button to increase the size of the balloon. With each pump after the first, the probability of balloon pop increases.
 - 4) Delay Discounting (DD).** The DD task measures decisional impulsivity. This task consists of two 15-minute runs, each of which comprises up to 150 trials. In each trial, a picture cue (either alcohol-related or neutral) is then shown. Each trial presents the participant with a choice between an immediate small reward or delayed larger reward.

5) Stop Signal Reaction Time Task (SSRT). The SSRT task consists of 3 x 10-minute blocks, each with up to 128 trials (~30 min for the 3 blocks). Participants must respond when shown a black square (Go Signal) but then must withhold their response if the color of the square changes to red. This task measures motor impulsivity and behavioral control.

